- ^m Please refer to Table 10 for PK blood sample collection schedule. The date and time of blood draw should be noted for all samples. Cycle 0 PK bloods samples may discontinue once sufficient safety and PK data has been collected. For patients who undergo intra-patient dose escalation, please collect pre-dose and 1 h at the time of escalation (Cycle X, Day 1) and after one cycle (Cycle X+1, Day 1). The PK collection for the food effect cohort is listed separately in Section 8.5.
- Please refer to Table 10 for urine PK sample collection schedule. The urine PK sampling may discontinue once sufficient safety and PK data has been collected.
- CCI
- P Collect samples pre-dose and 2 to 4 h post-dose AZD7648 on Cycle 1, Day 1 and Cycle 2, Day 1 only (or nearest weekly visit if within 2 days), note time of blood draw.
- ^q Only collect sample 2 to 4 h post–dose AZD7648 noting time of blood draw.
- ^r From Cycle 3 Day 1, sample should be taken on each radiological assessment (±7 days), disease progression or treatment discontinuation.
- ^s If any immune-related events are suspected, additional blood samples may be taken for further safety signal investigation.
- ^t Tumour assessments should be conducted every 8 weeks (±1 week) from start of treatment (Cycle 1, Day 1) until confirmed objective disease progression; frequency may be adjusted after 2 years of treatment if the tumour is not changing in size (complete response [CR], partial response [PR], or stable disease [SD]).
- ^u On clinic days, patients should not take the study treatment until instructed to do so by clinic staff.

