8 STUDY ASSESSMENTS AND PROCEDURES

Study procedures and their timing are summarised in the SoA.

The Investigator will ensure that data are recorded on the CRF. The Web Based Data Capture system will be used for data collection and query handling.

The Investigator ensures the accuracy, completeness and timeliness of the data recorded and of the provision of answers to data queries according to the Clinical Study Agreement. The Investigator will sign the completed CRF. A copy of the completed CRF will be archived at the study site.

Immediate safety concerns should be discussed with the Sponsor immediately upon occurrence or awareness to determine if the patient should continue or discontinue study treatment.

Adherence to the study design requirements, including those specified in the SoA, is essential and required for study conduct.

All screening evaluations must be completed and reviewed to confirm that potential patients meet all eligibility criteria. The Investigator will maintain a screening log to record details of all patients screened and to confirm eligibility or record reasons for screening failure, as applicable.

Procedures conducted as part of the patient's routine clinical management (eg, blood count) and obtained before signing of the ICF may be utilised for screening or baseline purposes provided the procedures met the protocol-specified criteria and were performed within the time frame defined in the SoA.

The number of samples taken, as well as the volume required for each analysis, may be changed during the study as emerging data become available. However, the estimated total volume of blood that will be drawn from each patient in this study during screening and the first cycle of treatment will not exceed approximately 350 mL (over a 1 month period). Any additional requirements are specified within the relevant section of Combination Module 1. Safety laboratory assessments will be performed locally at each centre's laboratory by means of their established methods. Therefore, the number of samples/blood volumes is patient to site-specific change.

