8.1 Efficacy assessments

8.1.1 Tumour assessments by CT or MRI

RECIST 1.1 guidelines for measurable and non-measurable TLs and non-target lesions (NTLs) and the objective tumour response criteria are presented in Appendix H of this protocol.

At baseline, the imaging modalities used for assessment should be contrast enhanced computed tomography (CT) (magnetic resonance imaging [MRI] where CT is contraindicated) scans of the brain, chest, abdomen and pelvis (including liver and adrenal glands) and should encompass all areas of known predilection for metastases in the disease under evaluation, and should additionally investigate areas that may be involved based on signs and symptoms of individual patients. Follow-up CT or MRI assessments will cover chest, abdomen and pelvis with any other regions imaged at baseline where disease was present. Any other sites at which new disease is suspected should also be appropriately imaged. A CT/MRI scan of the brain should be performed in all patients at the main screen.

Radiological examinations performed in the conduct of this study should be retained at site as source data. All treatment decisions will be based on site assessment of scans. Baseline radiological assessments should be performed no more than 28 days before the start of study treatment, and ideally should be performed as close as possible to the start of study treatment. Scans obtained as part of standard clinical practice, prior to informed consent, but within the 28-day period are acceptable. The radiological confirmatory scans should be performed no less than 4 weeks after the prior assessment of tumour and preferably at the next scheduled visit (in the absence of clinically significant deterioration).

The methods of assessment used at baseline should be used at each subsequent follow-up assessment through to objective confirmed radiological disease progression, as defined by

RECIST 1.1 and as determined by the Investigator. Tumour assessments should be performed every 8 weeks (2 cycles) (\pm 1 week) or earlier, if disease progression is suspected. If a patient discontinues treatment (and/or receives a subsequent cancer therapy) prior to progression then the patient should continue to be followed (unless they withdraw consent) until confirmed objective disease progression, as defined by RECIST 1.1. Scans confirming progression should not be conducted within 1 week after a progression biopsy to allow for reduction in inflammation.

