If scans are performed outside of scheduled visit window interval and the patient has not progressed, every attempt should be made to perform the subsequent scans at their scheduled visits whilst the patient remains on study treatment. If the patient interrupts treatment or incurs a treatment delay, scans should continue to occur at the protocol-defined frequency.

It is important to follow the assessment schedule as closely as possible. Please refer to the SoA.

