- Intrauterine system [IUS] device (eg, levonorgestrel releasing IUS -Mirena®) PLUS male condom.

• Intravaginal device (eg, EE and etonogestrel) PLUS male condom.

Appendix H Guidelines for Evaluation of Objective Tumour Response Using RECIST 1.1 Criteria (Response Evaluation Criteria in Solid Tumours)

Introduction

This Appendix details the implementation of response evaluation criteria in solid tumours (RECIST) 1.1 guidelines (Eisenhauer et al, 2009) for the study with regards to Investigator assessment of tumour burden including protocol-specific requirements for this study.

Definition of Measurable, Non-measurable, Target and Non-target Lesions

Patients with at least 1 lesion (measurable and/or non-measurable) that can be accurately assessed at baseline by computed tomography (CT), MRI or plain X-ray should be included in this study. Patients with previously irradiated TLs can be included in this study provided that there has been progression in the irradiated site following the treatment.

Measurable Lesions

A lesion, not previously irradiated, that can be measured accurately at baseline as ≥ 10 mm in the longest diameter (except lymph nodes) which must have a short axis ≥ 15 mm with CT or MRI and which is suitable for accurate repeated measurements.

Non-measurable Lesions

- All other lesions, including small lesions (longest diameter < 10 mm or pathological lymph nodes with ≥ 10 mm to < 15 mm short axis at baseline). Nodes with < 10 mm short axis are considered non-pathological and should not be recorded as non-target lesions (NTLs).
- Truly non-measurable lesions include the following: bone lesions, leptomeningeal disease, ascites, pleural/pericardial effusion, inflammatory breast disease, lymphangitic involvement of skin or lung, abdominal masses/abdominal organomegaly identified by physical examination that are not measurable by CT or MRI.
- Previously irradiated lesions as localised post-radiation changes, which affect lesion sizes, may occur. Therefore, lesions that have been previously irradiated will not be considered measurable and should be selected as NTLs at baseline and followed up as part of the NTL assessment.
- Skin lesions assessed by clinical examination.
- Brain metastasis.

Special Cases

• Lytic bone lesions or mixed lytic-blastic lesions, with identifiable soft tissue components, can be considered measurable if the soft tissue component meets the definition of measurability. Blastic lesions are considered non-measurable.

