Isotopic bone scans may be used as a method of assessment to identify the presence of new bone lesions at follow-up visits. New lesions will be recorded where a positive hot-spot that was not present on the baseline bone scan assessment is identified on a bone scan performed at any time during the study. The Investigator should consider the positive hot-spot to be a significant new site of malignant disease and represent true disease progression in order to record the new lesion. Confirmation by CT, MRI and X-ray is recommended where bone scan findings are equivocal.

FDG-PET Scan

FDG-PET (fluorodeoxyglucose positron emission tomography) scans may be used as a method for identifying new lesions, according with the following algorithm: New lesions will be recorded where there is positive FDG uptake (defined as when an uptake greater than twice that of the surrounding tissue is observed) not present on baseline FDG-PET scan or in a location corresponding to a new lesion on CT/MRI at the same follow-up visit. If there is no baseline FDG-PET scan available, and no evidence of new lesions on CT/MRI scans then follow-up CT/MRI assessments should be continued, scheduled as per protocol or clinical indicated, in order to confirm new lesions.

Tumour Response Evaluation

Schedule of Evaluation

Baseline tumour assessments should encompass all areas of known predilection for metastases in the disease under evaluation and should additionally investigate areas that may be involved based on signs and symptoms of individual patients and should be performed no more than 28 days before the start of study treatment. In Combination module 1, follow-up assessments should be performed every 8 weeks (± 1 week) after the start of treatment until discontinuation of study treatment or withdrawal of consent.

If AZD7648 is combined with any immuno-oncology drugs (in future combination modules) modified RECIST will be used in an exploratory analysis. If progression is not confirmed, then the overall visit response as per modified RECIST should be assessed as SD/partial response (PR) or CR and the patient should continue scheduled RECIST 1.1. CT/MRI scans. If progression is confirmed the overall visit response should be assessed as progressive disease as per modified RECIST.

Target Lesions

Documentation of Target Lesions

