To achieve 'unequivocal progression' on the basis of NTLs, there must be an overall level of substantial worsening in non-target disease such that, even in presence of SD or PR in TLs, the overall tumour burden has increased sufficiently to merit discontinuation of therapy. A modest 'increase' in the size of 1 or more NTLs is usually not sufficient to qualify for unequivocal progression status.

New Lesions

Details of any new lesions will also be recorded with the date of assessment. The presence of 1 or more new lesions is assessed as progression.

A lesion identified at a follow-up assessment in an anatomical location that was not scanned at baseline is considered a new lesion and will indicate disease progression.

The finding of a new lesion should be unequivocal: ie, not attributable to differences in scanning technique, change in imaging modality or findings thought to represent something other than tumour.

If a new lesion is equivocal, for example because of its small size, the treatment and tumour assessments should be continued until the new lesion has been confirmed. If repeat scans confirm there is a new lesion, then the progression date should be declared using the date of the initial scan.

Symptomatic Deterioration

Symptomatic deterioration is not a descriptor of an objective response: it is a reason for stopping study therapy.

Patients with 'symptomatic deterioration' requiring discontinuation of study treatment without objective evidence of disease progression at that time will undergo no further tumour

assessments in this study. Tumour response data for such patients will be censored at the date of their last RECIST assessment.

Evaluation of Overall Visit Response and Best Overall Response

The overall visit response will be derived using the algorithm shown in Table 4.

		NT T •	0 "
Target lesions	Non-Target lesions	New Lesions	Overall response
CR	CR	No	CR
CR	NA	No	CR
NA	CR	No	CR
CR	Non-CR/Non-progressive disease	No	PR
CR	NE	No	PR
PR	Non- progressive disease or NE	No	PR
SD	Non- progressive disease or NE	No	SD
NA	Non-CR/Non- progressive disease	No	SD (Non-CR/non- progressive disease)
NE	Non- progressive disease or NE	No	NE
NA	NE	No	NE
PD	Any	Yes or No	progressive disease
Any	progressive disease	Yes or No	progressive disease
Any	Any	Yes	progressive disease

Table 4Overall Visit Response

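### Protocol Appendix H stops tumour scans where Section 8.1.1, the SoA and the SAP continue them; where its symptomatic-deterioration rule was followed, Kaplan-Meier PFS would tend to be too high

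*Protocol*

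**What the plan says.** **Scans stop.** Protocol Appendix H, Symptomatic Deterioration, covers every module. Patients with symptomatic deterioration "requiring discontinuation of study treatment without objective evidence of disease progression at that time will undergo no further tumour" assessments, and "Tumour response data for such patients will be censored at the date of their last RECIST assessment". The same appendix, under Schedule of Evaluation, has Combination Module 1 patients scanned every 8 weeks "until discontinuation of study treatment or withdrawal of consent". Its introduction says it covers investigator "assessment of tumour burden including protocol-specific requirements for this study", so a site could not set it aside as generic RECIST text.

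**Scans continue.** Protocol Section 8.1.1 says that if treatment stops before progression, "the patient should continue to be followed (unless they withdraw consent) until confirmed objective disease progression". The Core Module SoA footnote schedules scans every 8 weeks "from start of treatment (Cycle 1, Day 1) until confirmed objective disease progression", and the Combination Module 1 footnotes for Parts A and B set the same endpoint. SAP Section 3.2.2.1.1 repeats that schedule. It adds, for patients who stop because of symptomatic progression, that assessments go on where possible until objective progression is seen.

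**Analysis.** Protocol Section 9.4.1 and SAP Section 3.2.2.1.6 define PFS regardless of withdrawal from therapy. Patients without an event are censored at the last evaluable RECIST assessment, and progression or death after two or more missed visits is also censored. SAP Section 4.2.2 reports Kaplan-Meier PFS with 80% confidence intervals and 3-monthly rates.

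**The concern.** A patient taken off treatment because of clinical worsening is probably nearer to progression than those still at risk. If scanning ends there, the patient leaves the risk set at the last progression-free scan. Kaplan-Meier estimation assumes that censored patients have the same outlook as those who remain, so such censoring is informative and PFS would tend to be too high. Duration of response could be affected too, because SAP Section 3.2.2.1.4 ends it at the PFS date.

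The SAP does not apply the Appendix H censoring sentence: its PFS section has no such rule. Any distortion therefore comes only from scans that were never taken, and no programming choice can restore them. SAP Section 6, which lists changes from the protocol, covers only PK symbols and does not note the difference.

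**Working it through.** The plan states no PFS figure to reproduce. The check has two parts.

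**1. One patient under each text (hypothetical).** The week 8 scan shows stable disease and treatment stops at week 12 for symptomatic deterioration.
- Section 8.1.1, SoA and SAP: the week 16 scan shows progression, so there is an event at week 16.
- Appendix H: there is no week 16 scan. Two scan intervals plus the 1-week window after week 8 end at 8 + 16 + 1 = week 25. Death at week 24 is an event, but later than week 16. Death at week 28 is censored back to week 8.

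Deaths therefore repair the loss only in part.

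**2. Size, by simulation** (400,000 patients per setting, Kaplan-Meier at 26 weeks).

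From the documents: 8-weekly scans; censoring at the last scan; deaths counted up to 17 weeks after it; median time to progression 15.9 weeks (Protocol Section 11.2.1.2, a PLD-treated ovarian population).

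Assumed, because the documents give no values: exponential progression time P; 10, 20 or 30% of patients stop at S = P − Uniform(0, L), with L = 0, 8, 16 or 24 weeks, and have no later scan; median survival after progression 13, 26 or 52 weeks.

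PFS with full scanning is 35.0%. The rise over all values of L is:

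| Affected | Rise in 26-week PFS (points) |
|---|---|
| 10% | 1.1 to 2.8 |
| 20% | 2.5 to 6.0 |
| 30% | 3.9 to 9.5 |

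The upper ends belong to L = 0, where progression is already present at the stop. Protocol Sections 8.1.1 and 9.4.1 provide for an earlier scan when progression is suspected. That scan would show it, and the Appendix H rule, which requires no objective evidence, would not apply. With L of 8 to 24 weeks the largest rise is about 8.3 points, so the usable range is about 1 to 8. With 6-week median survival after progression it is about 0.6 to 3.1.

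A separate simulation (median progression 12 weeks, stops up to 8 weeks before progression, 20-week survival after it, 10-30% affected) moved 6-month PFS from about 25% to 27-30% with deaths counted and to 27-34% with no later deaths captured.

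For stops unrelated to progression (the Combination Module 1 sentence, 10-30% affected), PFS was 35.1-35.3% without deaths and 33.0-35.0% with deaths counted, against 35.0%. There is no material upward shift.

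**Precision.** Core escalation cohorts have 1 to 6 patients (Protocol Section 9.2), and SAP Section 4.2 splits summaries by cohort and dose. At n = 6 one patient is 100/6 = 16.7 points. The 80% half-width at 35% is 1.2816 × √(0.35 × 0.65/n): 35.3 points at n = 3, 25.0 at n = 6, and 9.0 at n = 46 (all Core escalation patients pooled).

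**The case against.** The strongest reply is that sites had ample direction to keep scanning. Protocol Section 7.1 refers them to the SoA for follow-up after discontinuation. Section 7.1.3 says that stopping treatment does not end participation and that visits and data collection continue. Section 8 says "Adherence to the study design requirements, including those specified in the SoA, is essential and required for study conduct", and Section 8.1.1 adds "It is important to follow the assessment schedule as closely as possible. Please refer to the SoA". This stands as a limit on likelihood. None of it is a precedence clause, and Appendix H gives an explicit contrary instruction for a named group.

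A reader might infer that deaths are captured only in Part B, because Section 8.1.3 schedules survival follow-up there. That goes too far. Section 8.3.11 has deaths documented without limiting this to Part B, and Section 7.3 seeks vital status for all patients at study end. What remains is that Part A has no scheduled survival calls and that late deaths meet the two-missed-visits rule.

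A reader might also infer that missed post-baseline scans will go uncounted, because the categories named in SAP Section 2.3 mention only baseline RECIST scans. The documents do not support that: the complete list of important deviations is in a separate specification that is not available here.

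Finally, PFS is secondary, no hypothesis is tested (Protocol Section 9.1), Section 9.4.1 names ORR as the Part A efficacy measure, and development has been halted. All of this stands and limits importance.

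**Conclusion.** The contradiction is in current text and is certain. The bias is conditional: where sites followed the symptomatic-deterioration rule, Kaplan-Meier PFS, and possibly duration of response, would tend to be too high. On the assumptions above the rise is about 1 to 8 points on a 26-week PFS of 35%, or about 0.6 to 3 points if survival after progression is about 6 weeks. The fraction affected is unknown, so these are illustrations and not estimates for this trial.

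Stronger readings are not supported. The documents do not show that sites stopped scanning, so it cannot be said that the reported PFS is biased. No effect on ORR is claimed, and none for stops unrelated to disease. The 9.5-point figure should not be used, for the reason given in the working.

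Importance is minor to modest. It is worth acting on because SAP version 4.0 still reports PFS among limited efficacy outputs meant for publication. In single cohorts sampling error exceeds the bias, so the number of affected patients says more than a shifted curve.

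**What to change.** 1. Reconcile the two Appendix H passages, including the censoring sentence, with Section 8.1.1, the SoA and the SAP. This is one clarification; it cannot recover scans already missed.
2. Report by module how many patients stopped treatment without RECIST progression and had no later scan. Discontinuation reasons and days (Protocol Section 9.4) and patient-level tumour assessments (SAP Section 4.2.2) are already to be listed, so no new data are needed. With development halted, this is the most useful step.
3. Only if that number is above zero, add one PFS sensitivity analysis. It counts discontinuation for disease progression or symptomatic deterioration, without RECIST progression, as an event at the discontinuation date. Protocol Section 7.1 groups these reasons, so check each against the RECIST data.

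Show that analysis beside the main estimate as a conservative sensitivity analysis, not as a correction. Nor is it a guaranteed lower bound. In the simulation the stop never falls after the event that full scanning would give, but only because S was built from P. In practice an earlier scan may be missed or not evaluable, and a stop can then fall after the date on which that scan would have shown progression.

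The cost is one clarification, one count and at most one extra analysis. The downside is that the sensitivity analysis may be up to about 5 points low (4.8 at most, over median progression times of 8 to 24 weeks), which is comparable with the bias it addresses. It also does not deal with informative stops for other reasons.

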Appendix I Food Effect Cohort Plan

Summary

- The food effect cohort of the study comprises a cross over design.
- Each patient in the food effect cohort will initially receive a single oral dose of AZD7648 (dose to be decided by the SRC) on Cycle 0, Day 1 in either the fasted or fed state. The Parexel project manager (in appropriate consultation with AZ study team) will advise each site on whether a particular patient participating in the food effect cohort has been allocated to the fed or fasted group for their Cycle 0, Day 1 dose.
- The patient will then cross over to receive their single Cycle 1, Day 1 dose in the opposite state to their Cycle 0, Day 0 dose. So, if the patient had the Cycle 0, Day 1 dose in the fasted state, the Cycle 1, Day 1 dose will be taken in the fed state, after a high fat breakfast meal. If the patient had the Cycle 0, Day 1 dose in the fed state, the Cycle 1, Day 1 dose will be taken in the fasted state (water only for ≥2 hours prior to taking a dose to ≥1 hour post-dose). The Cycle 1, Day 1 dose should be given in the morning at least 72 hours after the Cycle 0, Day 1 dose.

Meal and Timing Requirements

- Please note that for the fasted state, patients must fast (water only) for ≥ 10 hours prior to taking a dose to ≥ 2 hour post-dose. For the fed state patients must fast overnight (minimum of 10 hours) prior to consuming a standardised meal in the clinic.
- For the fed dosing day, the meal should consist of about 800 to 1000 total calories, with around 54% of the calorific content made up from fat. The dose should be administered with 240 mL of water.
- Patients should ideally start the recommended meal 30 min prior to planned administration of the study drug and aim to consume at least 75% of the meal within 30 min.
- If the patient takes less than 30 min to complete the meal, it is still expected that the drug is dosed not earlier than 30 min after the start of the meal.
- If the patient is unable to consume at least 75% of the meal within 30 min an additional 15 min will be allowed.
- The study drug should be administered after a minimum of 75% of the meal is completed between 30 min and up to 45 min after starting the meal.
- Please note that patients will only be considered evaluable for the food effect cohort if they eat at least 75% of their meal within a maximum of 45 min. Patients will remain in the Part A continuous scheduling cohort and should continue to receive their dose and undergo planned sampling/procedures even if they have been unable to consume the required amount of food within the 45 min window, but will not be considered evaluable for the food effect cohort.
- After Cycle 1, Day 1 patients may continue to receive AZD7648 monotherapy (continuous dosing) and all dosing from that point onwards must be administered in the fasted state.

- Pharmacokinetic samples will be taken at the times indicated in the study protocol.
- Please note that patients with insulin-dependent diabetes must be excluded from the food effect cohort(s). Eligibility of patients with Diabetes Type I or uncontrolled Type II (HbA1c > 7 mmol/L assessed locally) will be judged by the Investigator.

Summary of 5 High-fat Breakfast Meals

In accordance with FDA guidance (FDA Guidance for Industry 2002), the high fat meal should have a total of approximately 800 to 1000 kcal, with approximately 50-60% of the calorific content made up from fat. The meal should therefore derive approximately 150, 250 and 500 to 600 kcal from protein, carbohydrate and fat respectively, as shown in Table 1.

Some high fat breakfast meal examples are given in Table 2 to Table 6. The exact composition of the meal may vary as long as the totals are similar to those detailed in Table 1.

	Protein (kcal)	Carbohydrate (kcal)	Fat (kcal)	Total (kcal)	Fat (%)
Target	150	250	500-600	800-1000	50
Regular	215	266	543	1000	54.3
Gluten Free	197.2	232	497	890	53.5
Lactose Free	198	252	504	956	53
Vegetarian	161.4	208	449	800	56

Table 1Calorie Composition

Table 2Regular High Fat

	Kcals	Fat	СНО	Protein
1 cup whole milk	150	8	12	8
1/2 cup cheerios (1 container)	70	1	14	1
1/2 slice French toast	110	3.5	15.5	4.5
2 turkey sausage patties	160	12	-	14
3.5 oz scrambled eggs	160	11.89	4	13.36
2 slices provolone cheese	160	12	2	10
1 slice toast	80	1	15	3
3 packets butter	100	11	-	-
1 sugar free syrup	10	-	4	-

	Kcals	Fat	СНО	Protein
Totals		60.39g	66.5g	53.86g
	1000 kcal	543 kcal	266 kcal	215 kcal
		54.3% kcals	26.6% kcals	21.5% kcals

Table 3Gluten Free High Fat

	Kcals	Fat	СНО	Protein
1 cup whole milk	150	8	12	8
3/4 cup cereal (rice chex 1 container)	70	-	16	1
1 slice gluten-free bread	120	2.5	23	2
1 pouch cream cheese	70	7	1	1
2 turkey sausage patties	160	12	-	14
3.5 oz scrambled eggs	160	11.89	4	13.36
2 slices provolone cheese	160	12	2	10
Totals		53 g	58g	49.3g
	890 kcals	477 kcal	232 kcals	197.2 kcals
		53.5%	26%	22%

Table 4Lactose Free High Fat

1 cup Lactaid whole milk	160	8	13	8
2 hard-boiled eggs	156	10	2	12
3 turkey sausage	240	18	-	21
1 slice whole grain toast	120	3	19	5
3 packets butter	100	11	-	-
¹ / ₂ Belgium waffle	170	6	25	3.5
1 sugar free syrup	10		4	
Totals	956 kcals	56g	63g	49.5g
		504 kcal	252 kcal	198 kcal
		53%	26.3%	20.7%

Table 5Vegetarian High Fat

1 cup whole milk	150	8	12	8
1 slice French toast	220	7	31	9
1 sugar free syrup	10	-	3	-
3 packets butter	100	11	-	-
3.5 oz scrambled eggs	160	11.89	4	13.36
2 slices provolone cheese	160	12	2	10
Totals		49.89 g	52g	40.36g
	800 kcals	449 kcal	208 kcal	161.4 kcal
		56%	26%	20%

Table 6Continental Breakfast

	Kcals	Fat	СНО	Protein
Tea/ coffee	0	0	0	0
Yogurt	176	13	7	6
Cheese	152	11	0	11
Bread	110	0	24	3
1 croissant	189	9	23	4
butter	147	16	0	0
sugar	40	0	10	0
Ham (2 slices)	143	7	0	20
Totals		57	64	45
	959 kcals	519 kcals	258 kcals	181 kcals
		54%	27%	19%

FDA Guidance for Industry 2002

Food-Effect Bioavailability and Fed Bioequivalence Studies. U.S. Department of Health and Human Services Food and Drug Administration Center for Drug Evaluation and Research (CDER). December 2002. Available at:

https://www.fda.gov/downloads/drugs/guidancecomplianceregulatoryinformation/guidances/u cm070241.pdf. Accessed 16 October 2018.

Appendix J Changes Related to Mitigation of Study Disruptions Due to Cases of Civil Crisis, Natural Disaster, or Public Health Crisis

Note: Changes below should be implemented only during study disruptions due to any of or a combination of civil crisis, natural disaster, or public health crisis (eg, during quarantines and resulting site closures, regional travel restrictions and considerations if site personnel or study patients become infected with SARS-CoV-2 or similar pandemic infection) during which patients may not wish to or may be unable to visit the study site for study visits. These changes should only be implemented if allowable by local/regional guidelines and following notification from the Sponsor and instructions on how to perform these procedures will be provided at the time of implementation.

J 1 Reconsent of Study Patients During Study Interruptions

During study interruptions, it may not be possible for the patients to complete study visits and assessments on site and alternative means for carrying out the visits and assessments may be necessary, eg, remote visits. Reconsent should be obtained for the alternative means of carrying out visits and assessments and should be obtained prior to performing the procedures described in Sections J 2 to J 5. Local and regional regulations and/or guidelines regarding reconsent of study patients should be checked and followed. Reconsent may be verbal if allowed by local and regional guidelines (note, in the case of verbal reconsent the informed consent form [ICF] should be signed at the patient's next contact with the study site). Visiting the study sites for the sole purpose of obtaining reconsent should be avoided.

J 2 Rescreening of Patients To Reconfirm Study Eligibility

Additional rescreening for screen failure due to study disruption can be performed in previously screened participants. The investigator should confirm this with the designated study physician.

In addition, during study disruption there may be a delay between confirming eligibility of a patient and either enrolment into the study or commencing of dosing with investigational product. If this delay is outside the screening window specified in in the appropriate Schedule of Assessment Table, the patient will need to be rescreened to reconfirm eligibility before commencing study procedures. This will provide another opportunity to re-screen a patient in addition to that detailed in Section 5.4.

J 3 Home or Remote Visit to Replace On-site Visit (where applicable)

A qualified Health Care Professional (HCP) from the study site or third-party vendor service will visit the patients home / or other remote location as per local standard operating

procedures (SOPs), as applicable. Supplies will be provided for a safe and efficient visit. The qualified HCP will be expected to collect information per the clinical study protocol (CSP).

J 4 Telemedicine Visit to Replace On-site Visit (where applicable)

In this appendix, the term telemedicine visit refers to remote contact with the patients using telecommunications technology including phone calls, virtual or video visits, and mobile health devices.

During a civil crisis, natural disaster, or public health crisis, on-site visits may be replaced by a telemedicine visit if allowed by local/regional guidelines. Having a telemedicine contact with the patients will allow adverse events, concomitant medication, Eastern Cooperative Oncology Group performance status (ECOG PS) to be reported and documented.

J 5 At-home or Remote Location IP Administration Instructions

If a site visit is not possible, at-home or remote location administration of investigational product may be performed by a qualified HCP, provided this is acceptable within local regulation/guidance, or by the patient or his/her caregiver. The option of at-home or remote location investigational product administration ensures patients safety in cases of a pandemic where patients may be at increased risk by traveling to the site/clinic. This will also minimize interruption of investigational product administration during other study disruptions, eg, site closures due to natural disaster. All necessary supplies and instructions for administration and documentation of investigational product administration will be provided if site is able to complete all safety assessments as per CSP.

J 6 Data Capture During Telemedicine or Home / Remote Visits

Data collected during telemedicine or home / remote visits will be captured by the qualified HCP from the study site or third-party vendor service, or by the patient themselves eg, details of self-administration of study medication in diary card.

